8.7 Time to Progression in patients with bone metastases

Majority of the patients with prostate cancer have bone metastases which are not considered measurable sites of disease. Progression in patients with bone metastases will be defined as either the appearance of a minimum of 2 new lesions on bone scan which are related to metastatic disease per the judgement of the treating physician, or the occurrence of a new skeletal related event or by PSA criteria per PCWG 2. Skeletal-related event is defined as occurrence of new pathologic bone fractures (vertebral or nonvertebral), spinal cord compression, requirement of surgery or radiation therapy to bone metastases (including the use of radioisotopes), or a requirement to change antineoplastic therapy to treat bone pain or other related symptoms.

8.8 Progression Free Survival

Time from registration to PSA progression as defined by PCWG 2 criteria or measurable disease progression by RECIST1.1 or skeletal disease progression by appearance of new metastatic sites on bone scan or clinical progression as determined by treating physician assessment, or death from any cause, whichever occurs first.

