| creat | X | X | | | X | | | X | | X | |
| PT/INR ² | X | X | X | X | X | X | X | X | X | X | |
| PSA | X | X | X | X | X | X | X | X | X | X | |
| Testosterone | X | | | | X | | | X | | X | |
| CXR/CT ³ | X | | | | | | | X | | | |
| Bone ³ scan | X | | | | | | | X | | | |
| OS | | | | | | | | | | | X |
| Progression | | X | X | X | X | X | X | X | X | | X |
| Tumor biopsy ⁵ | X ⁵ | | X ⁵ | | | | | | | | |
| CTC ⁵ | | X ⁵ | X ⁵ | | | | | | | | |

1. Pre-study H & P, labs, EKG may be done within 28 days of registration. If Labs, and H and P are done within 72 hours prior to registration=they do not have to be repeated on day 1 of therapy unless clinically indicated.
2. PT, INR to be done only if patient on therapeutic Coumadin and then will need to be repeated at least once every month.
3. Tumor assessment scans must be within 60 days prior to registration for all patients. Bone scans are required for pretreatment and subsequent tumor assessments. CT/MRI of abdomen and pelvis should be done if necessary for tumor assessment. Radiologic assessment with bone scans should be done at 6 and

12 months on study (+/- 1 month) and then annually (+/- 1 month) as long as patient continues on study treatment. For late induction registrations, tumor assessment imaging showing metastatic disease must be available prior to start of androgen deprivation therapy.

4. After completion of therapy patients will be followed every 3 months for disease status and survival.
5. Fresh tissue should be collected pre-therapy. Archival tissue should be submitted within 28 days of registration. Post treatment tumor biopsy (optional) and CTC can be conducted within 28-42 days after registration even for late induction patients. Late induction patients will get CTC at time of study entry and then 28-42 days later.
6. Disease progression is defined as evidence of radiographic progression, a skeletal-related event, or clinical progression. Progression of measurable disease is defined by RECIST 1.1 criteria, or progression of bone metastases or occurrence of new skeletal related event or by PSA per PCWG 2 criteria [Appendix B].

8.0 CRITERIA FOR EVALUATION AND ENDPOINT DEFINITION:

The RECIST 1.1 criteria with unidimensional measurement are to be used for measurable disease response evaluation [14].

Baseline Disease Assessment

Measurable lesions must be accurately measured in at least one dimension

(longest diameter in the plane of measurement is to be recorded) with a minimum size of:

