8.2 Response Rate

For measurable disease response, RECIST 1.1 criteria will be used. The Prostate Cancer Clinical Trials Working Group (PCWG2) criteria will be used to determine a PSA response [15]. PCWG2 recommends a two-objective paradigm in metastatic CRPC: (1) controlling, relieving, or eliminating disease manifestations that are present when treatment is initiated and (2) preventing or delaying disease manifestations expected to occur. PSA decline, changes in imaging will also be reported. The progression for measurable disease will be per RECIST1.1 criteria, and for bone metastases will be per PCWG2.

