8.4 Duration of stable disease

Stable disease is measured from the start of the treatment until the criteria for progression are met, taking as reference the smallest measurements recorded since the treatment started. Tumor evaluations are recommended every three cycles while on protocol therapy and then as clinically required by the treating physician.

8.5 Time to Treatment Failure:

From date of registration to date of progressive disease, or date patient is taken off study for any reason. All patients, regardless of the number of completed cycles of therapy, will be included for toxicity evaluation. All subjective toxicities encountered during the study will be evaluated according to the NCI toxicity criteria. Objective toxicities will be based upon the greatest severity that occurred at any time during a treatment cycle and not on the severity noted at the beginning of the next cycle.

8.6 Time to Progression:

From date of registration to date of progressive disease, defined as either progression of measurable disease by RECIST 1.1 criteria, or progression of bone metastases or occurrence of new skeletal related event or by PSA per PCWG 2 criteria [Appendix B].

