8.12 Skeletal-related event

Defined as occurrence of new pathologic bone fractures (vertebral or nonvertebral), spinal cord compression, requirement of surgery or radiation therapy to bone metastases (including the use of radioisotopes), or a requirement to change antineoplastic therapy to treat bone pain or other related symptoms.

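### A skeletal-related event counts as progression for TTP but is not named for PFS, so PFS can run longer than TTP in the same patient

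*Combined protocol and SAP*

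**What the plan says.** Four places in the combined protocol and SAP define progression.

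- **Section 8.6 (TTP).** After RECIST 1.1 progression of measurable disease, the list continues "or progression of bone metastases or occurrence of new skeletal related event or by PSA per PCWG 2 criteria". Neither clinical progression nor death is named.
- **Section 8.7 (TTP in patients with bone metastases).** The bone-scan criterion is "the appearance of a minimum of 2 new lesions on bone scan", judged metastatic by the treating physician, "or the occurrence of a new skeletal related event or by PSA criteria per PCWG 2". RECIST is not part of this endpoint.
- **Section 8.8 (PFS).** The components are "PSA progression as defined by PCWG 2 criteria or measurable disease progression by RECIST1.1", then "skeletal disease progression by appearance of new metastatic sites on bone scan or clinical progression as determined by treating physician assessment", then death from any cause. SREs are not named, and no number of new sites is given.
- **Study calendar (7.0), footnote 6.** The first sentence reads "Disease progression is defined as evidence of radiographic progression, a skeletal-related event, or clinical progression". The second repeats the 8.6 list, without clinical progression.

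Section 8.2 adds that progression "for bone metastases will be per PCWG2". Section 11.3.4 sends each time-to-event endpoint back to its own Section 8 definition, and 11.6.4 compares each by arm with a stratified log-rank test. Nothing in Section 11 reconciles the definitions.

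**The concern.** PFS is normally the TTP event or death, whichever comes first, so in any one patient it cannot fall after TTP. That ordering fails if TTP counts something that PFS does not. Here TTP counts an SRE, and PFS reaches one only through the physician's view that it is also clinical progression.

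The case is not contrived. Radiation to a bone metastasis is an SRE under 8.12. Palliative radiation is permitted by inclusion criterion 3 in 4.1, and 5.3 says radiation should not lead to stopping study drug. A patient treated in this way has a TTP event, may remain on therapy, and has no PFS event under 8.8 unless clinical progression is declared.

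At stake is whether two secondary endpoints, each tested between arms, can be interpreted together. If TTP and PFS differ in the results, a reader could not tell whether treatment or the definitions caused it. Leaving the choice open also invites a decision between definitions after the data are seen.

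**Working it through.** **The plan's own figure.** No event count, power or sample size is given for TTP or PFS. The only sample size is for the primary PSA endpoint (11.5): 50% versus 75%, one-sided 0.10, power 0.80, 1:1. With mean proportion 0.625:

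- n = [1.2816·√(2·0.625·0.375) + 0.8416·√(0.5·0.5 + 0.75·0.25)]² / 0.25² = (0.8774 + 0.5567)² / 0.0625 = 32.9.
- With continuity correction: (32.9/4)·[1 + √(1 + 4/(32.9·0.25))]² = 40.5, so 41 per arm.
- Allowing 10% non-evaluable: 41/0.9 = 45.6, so 46 per arm and 92 in total.

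The stated 41, 46 and 92 are reproduced. They do not depend on TTP or PFS.

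**The definitions side by side.** The bone component of 8.6 is taken from 8.7, the only place that gives it a number.

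| Component | TTP (8.6 with the 8.7 bone rule) | PFS (8.8) | Footnote 6 |
|---|---|---|---|
| RECIST 1.1 | yes | yes | yes |
| PSA per PCWG2 | yes | yes | yes |
| New bone-scan lesions | at least 2 | number not given | number not given |
| New SRE | yes | not named | yes |
| Clinical progression | not named | yes | yes, first sentence only |
| Death | no | yes | no |

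**Enumeration.** Take PSA progression, RECIST progression, SRE, clinical progression and death as present or absent, and new bone-scan lesions as 0, 1, or 2 or more. That gives 2⁵ × 3 = 96 patterns, each classified under both definitions.

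1. *TTP event but no PFS event, reading 8.8 as any new site:* one pattern. It is an SRE with no PSA or RECIST progression, no new lesion, no declared clinical progression and no death.
2. *The same, reading 8.8 as at least 2 sites:* two patterns, namely the same SRE with 0 or 1 new lesion. The gap exists on either reading and comes only from the SRE.
3. *PFS event but no TTP event, patient alive, any-site reading:* three patterns. They are one new lesion alone, clinical progression alone, and the two together. On the 2-site reading, only those with clinical progression remain (0 or 1 new lesion).
4. *With SRE added to PFS and the 2-lesion rule in both:* no pattern has a TTP event without a PFS event.

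**Timing.** If an SRE occurs at time t₁ and PSA progression at a later t₂, with nothing else in between, TTP = t₁ and PFS = t₂, so PFS exceeds TTP.

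**Size.** The number of affected patients would need the share of first events that are SREs alone, single new lesions alone, or clinical progression alone. The documents give none of these.

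**The case against.** **Clinical progression will pick up the SREs.** This is partly right. The SRE definition includes a change of antineoplastic therapy for bone pain, which a physician would plausibly call clinical progression. It would be wrong to infer that an SRE can never be a PFS event. But the first sentence of footnote 6 lists an SRE and clinical progression as separate items, so the one does not automatically imply the other, and capture is discretionary.

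**Section 8.2 already imposes PCWG2 on bone progression.** This stands as far as it goes. A reader might infer from 8.8 that a single new lesion is definitely a PFS event. The text is an unnumbered plural, and 8.2 may govern it, so that is one reading only. However, 8.8 cites PCWG2 only for PSA, Appendix B reproduces only the PSA rule, and 8.2 does nothing about the missing SRE.

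**The lesion-count difference.** A reader might also blame this for patients who progress for TTP but not PFS. It cannot do that: it works in the other direction, as does clinical progression.

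**Bias by arm.** A reader might infer that unblinded judgement favours one arm. The protocol describes no blinding or placebo (four capsules against one tablet), so differential judgement is possible. But 8.7 also relies on physician judgement, SREs include treatment decisions, and nothing in the documents shows a difference by arm or a changed ranking.

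**Low stakes.** These are two of seven secondary time-to-event endpoints in a screening design that 11.4.1 calls non-definitive. That limits the weight of the point but does not remove it, because both endpoints are formally compared.

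**Conclusion.** The inconsistency is real and follows from the text alone. TTP counts an SRE and PFS does not name it, so PFS can exceed TTP in the same patient. Separately, a patient can have a PFS event without a TTP event through clinical progression or, on one reading of 8.8, a single new bone-scan site.

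It is tempting to turn this into a lengthening of median PFS. With exponential times and an assumed SRE share of 10% to 30% of first events, dropping SREs multiplies the median by 1/0.9 = 1.11 to 1/0.7 = 1.43. The documents do not support that as a statement about PFS. The share is assumed, and the calculation ignores everything that 8.8 adds (death, clinical progression and possibly single lesions), all of which shorten PFS. Size and net direction therefore remain unknown.

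The conclusion assumes that the bone component of 8.6 means the rule in 8.7. The SRE gap does not depend on that assumption. The primary endpoint and the 82 evaluable or 92 enrolled patients are untouched. The point merits correction before analysis, as a matter of coherence between tested secondary endpoints.

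**What to change.** For endpoint analysis only:

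- Use the same progression components in 8.6 and 8.8: RECIST 1.1, the bone-scan rule already in 8.7, a new SRE as defined in 8.12, and PSA per Appendix B.
- Define PFS as the first of these or death from any cause.
- Treat clinical progression the same way in both endpoints, or keep it out of both main definitions and use it in a PFS sensitivity analysis.
- Keep 8.7 bone-specific. Copying the full list into it would add RECIST progression and change that endpoint.
- Reconcile footnote 6, whose two sentences differ, with these sections. Disease progression is also a removal criterion (9.4), so this should be done without the endpoint wording setting a rule for stopping treatment.

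The cost is a wording change in Section 8, made before analysis. No new assessments should be needed: 11.3.7 already follows patients for SREs until SRE, PSA progression or death, and the calendar already includes progression. The case report forms are not among the documents, so the sponsor should confirm that SRE dates and clinical-progression calls are recorded separately.

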Karmanos Cancer Institute. Training and support will be provided for all staff entering data. Data entry must occur within 2 weeks of visits along with submission of applicable source documentation. The only concomitant medication data to be submitted is administration of bisphosphonate or denosumab.

5.2 Stratification and randomization procedures:

The registering data manager will first stratify the patient by race (AA or other) and cancer related bone pain at diagnosis of metastatic disease (present or absent) into one of 4 strata. Even if pain is well controlled/resolved at present the patient will be considered positive for bone pain. The patient will then be randomized to Arm A or Arm B using the stratum-appropriate randomization list prepared in advance by the study statistician [name]. Arms A and B are defined in the Study Schema (on page 5) and in Section 5.3 below. Each of the 4 randomization sequences will use random permuted blocks of varying sizes. The treatment arm randomization and enrollment confirmation will be communicated to site staff in writing within 24-48 hours from receipt of all eligibility source documents. Study treatment should start within 7 days of registration.

5.3 Study design and plan:

Overall Study Design and Plan

This study is a multicenter Phase II, randomized, screening study of oral MDV3100 (160 mg/day) in patients with metastatic hormone sensitive prostate cancer. Patients must not have received prior cytotoxic chemotherapy for metastatic disease. Radiation therapy, and initiation of

bisphosphonates or other approved bone targeting agents, and standard of care steroid and pain management are allowed and should not result in discontinuation of study drug therapy.

For patients eligible for late induction registration the treatment start date will be the date of initiation of GNRH analogue or antagonist, with or without antiandrogen. Late induction patient visits will be adjusted based on the length of their prior hormone therapy. Study drug therapy should be continued as long as the patient is tolerating the study drug and continues androgen deprivation therapy or until confirmed radiographic disease progression or a skeletal related event AND one of the two following events: 1) initiation of another agent for treatment of prostate cancer. Or 2) Intolerance to therapy.

Patients will be randomized to receive either:

ARM A

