5.4 Agent Administration

Starting doses of the agents are as follows:

Enzalutamide is provided as 40 mg soft gelatin capsules in bottles with induction-sealed childresistant caps.

Directions for Administration

Study drug doses should be taken as close as possible to the same time each day. All study patients on enzalutamide will take 4 capsules of study drug once daily unless dose adjustment has been done. Patients randomized to bicalutamide will take 1 tab of 50 mg daily dose. If dosing is missed on one day for any reason, double-dosing should NOT occur the following day. The oral medications can be taken with or without food. Documentation of daily dose will be conducted by patient on a study diary.

Storage and Labeling

Study drug should be stored in a secure location with limited access within the following temperature range: 59°F to 86°F (15°C to 30°C). Bottles will be labeled with the study protocol number, medication or bottle number, contents, directions for use, storage directions. Patients will be instructed to store study drug at room temperature out of the reach of children.

6.0 TOXICITIES TO BE MONITORED AND DOSAGE MODIFICATION:

All toxicities will be graded as per NCI Common Toxicity (CTCAE) version 4.0.

Toxicity evaluation will be done monthly for the first 8 visits starting with day 1 and after that every 3 months until progression. Radiologic evaluation at months 6 and 12 with scans (CT scans and bone scan), and PSA levels every month for the first 8 visits and after that every 3 months. After 12 months radiologic evaluation is required annually while patient is on study.

Dose Reduction/Dose Adjustment

Patients who experience a Grade 3 or greater toxicity that is attributed to study medication, and cannot be ameliorated by the use of adequate medical intervention should have their treatment interrupted until the toxicity improves to a Grade 2 or lower severity. Patients may subsequently be re-started on study drug, including at a reduced dose (80 mg daily of enzalutamide), with the written approval of the PI (or designee). **Any reports of seizure activity for patients randomized to enzalutamide require immediate and permanent discontinuation of this therapy.**

There are no dosage adjustments for hematologic toxicity.

Dosage adjustments for Non-hematologic Toxicity: a.

Diarrhea Toxicity:

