All lesions (or sites of disease) not identified as target lesions, including pathological lymph nodes and all non-measurable lesions, should be identified as non-target lesions and be recorded at baseline. Measurements of these lesions are not required and they should be followed as 'present', 'absent' or in rare cases, 'unequivocal progression'.

Evaluation of target lesions

Complete Response (CR): Disappearance of all target lesions. Any pathological lymph nodes (whether target or non-target) must have reduction in short axis to <10 mm.

Partial Response (PR): At least a 30% decrease in the sum of diameters of target lesions, taking as reference the baseline sum of diameters.

Progressive Disease (PD): At least a 20% increase in the sum of diameters of target lesions, taking as reference the smallest sum on study (this may include the baseline sum). The sum must also demonstrate an absolute increase of at least 5 mm.

Stable Disease (SD): Neither sufficient shrinkage to qualify for PR nor sufficient increase to qualify for PD.

Confirmation

In non-randomized trials where response is the primary endpoint, confirmation of PR and CR is required to ensure responses identified are not the result of measurement error. This will also permit appropriate interpretation of results in the context of historical data where response has traditionally required confirmation in such trials. However, in all other circumstances, (i.e., in randomized phase II or III trials or studies where stable disease or progression are the primary endpoints), confirmation of response is not required since it will not add value to the interpretation of trial results. However, elimination of the requirement for response confirmation may increase the importance of central review to protect against bias, in particular in studies which are not blinded. In the case of SD, measurements must have met the

SD criteria at least once after study entry at a minimum interval (in general not less than 6–8 weeks) that is defined in the study protocol.

8.1 Primary Endpoint:

The proportion of patients on either arm achieving a PSA nadir of 4 or less (< 4 ng/ml) at month 7 of protocol therapy.

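### PFS counts undefined clinical progression, called by a physician who knows the arm, as an event on its own, and no PFS analysis without that component is planned

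*Combined protocol and SAP*

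**What the plan says.** Section 8.8 defines PFS as the time from registration to the first of PCWG2 PSA progression, RECIST 1.1 progression, new metastatic sites on bone scan, "clinical progression as determined by treating physician assessment", or death. The components are alternatives, so a clinical call alone is enough. No section gives criteria for it. Footnote 6 to the Study Calendar (Section 7.0) uses the term again, also without criteria: "Disease progression is defined as evidence of radiographic progression, a skeletal-related event, or clinical progression".

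The words open-label do not appear, but Section 5.2 says: "The treatment arm randomization and enrollment confirmation will be communicated to site staff in writing within 24-48 hours". Section 5.4 describes visibly different regimens: "All study patients on enzalutamide will take 4 capsules of study drug once daily unless dose adjustment has been done", and "Patients randomized to bicalutamide will take 1 tab of 50 mg daily dose". No placebo, masking or blinded assessor is described.

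Section 11.6.4 gives all time-to-event endpoints the same treatment: Kaplan-Meier estimates and a log-rank test stratified by race and bone pain. It contains no sensitivity analysis for PFS.

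**The concern.** When the assessor knows the treatment and the event has no written criteria, the threshold for calling it can differ between arms. A difference in PFS could then partly reflect when physicians chose to call progression. The schedule leaves room for this. Under Section 6.0, scans are at months 6 and 12 and then annual, while PSA and toxicity checks after the first eight visits are every 3 months, so a clinical call can come well before the next scan and set the event date.

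At stake is how far a PFS difference can be trusted when it is read beside the primary result in deciding whether to plan a larger study. If the triggering component is not recorded during the trial, the question may not be answerable afterwards.

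**Working it through.** **1. What is not affected.** The only sizing in the plan is for the PSA endpoint (Section 11.5): 50% against 75%, one-sided 0.10, power 0.80, Fleiss method.
- Uncorrected: n = [1.2816·√(2·0.625·0.375) + 0.8416·√(0.5·0.5 + 0.75·0.25)]² / 0.25² = 1.434² / 0.0625 = 32.9.
- Continuity-corrected: (32.9/4)·[1 + √(1 + 4/(32.9·0.25))]² = 40.5, so 41 per arm, as stated.
- Allowing 10% non-evaluable: 41/0.9 = 45.6, so 46 per arm and 92 in total, as stated.

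None of this involves PFS. The documents give no event count, hazard ratio, alpha or power for PFS.

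**2. Do the other endpoints already show the effect?**

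| Component | PFS (8.8) | TTP (8.6) | OS (8.9) |
|---|---|---|---|
| PSA progression, PCWG2 | yes | yes | no |
| RECIST 1.1 progression | yes | yes | no |
| Bone progression | new sites on bone scan | yes | no |
| Stand-alone clinical progression | yes | no | no |
| Skeletal-related event | not listed | yes | no |
| Death | yes | no | yes |

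TTP drops the clinical call but also drops death and adds skeletal-related events. Section 8.12 counts as such an event a requirement to change antineoplastic therapy for bone pain or related symptoms, which is again a physician's decision. PFS and TTP thus differ in three components at once, and a gap between them cannot be attributed to clinical calls.

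**3. Illustration by simulation.** All inputs except the 46 per arm are assumptions or choices made here:
- No true difference; exponential PFS with a 12-month median.
- Uniform accrual over 32 months (within the 27 to 37 months of Section 11.7.2), then 12 months of follow-up.
- One-sided 0.10 log-rank test, borrowed from the primary endpoint.
- A clinical call moves the event to 30% to 90% of its true time in a stated share of patients.
- 6,000 trials per scenario, giving about 72 events per trial.

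| Early calls, Arm A / Arm B | False-positive rate | Apparent HR |
|---|---|---|
| 5% / 5% | 0.10 | 1.00 |
| 15% / 15% | 0.10 | 1.00 |
| 5% / 15% | 0.14 | 0.95 |
| 5% / 20% | 0.16 | 0.93 |
| 5% / 25% | 0.19 | 0.91 |

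Repeat runs agree within about 0.01. Shortening follow-up to the 7 months of Section 11.7.3 changes little.

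**4. A second model, in closed form.** Let clinical-only progression be a share s of the Arm A event hazard, over-called in Arm B by a factor r, with no true effect. Then HR = 1/[(1 − s) + s·r], and the false-positive rate with d events is 1 − Φ(1.2816 − √(d/4)·|ln HR|).
- s = 0.20, r = 1.5: HR = 1/(0.80 + 0.30) = 0.909; the rate is 0.172 at 50 events and 0.189 at 70.
- Across s = 0.05 to 0.30 and r = 1.25 to 2.0, HR runs from 0.99 to 0.77 and the rate from 0.11 to 0.43.
- At r = 1, HR = 1 and the rate stays at 0.10.

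Both models say the same thing: the effect depends on how unequal the calling is, and the documents are silent on that.

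**The case against.** The strongest reply is about weight. PFS is one of seven secondary time-to-event endpoints in a design that Section 11.4.1 calls non-definitive, and the decision on a larger study is tied there to the primary endpoint. Including clinical progression in PFS is a legitimate choice. TTP omits the stand-alone clinical call and gets the same test, and OS needs no progression judgement, so a PFS effect absent from both would be a visible warning. All of this stands. It rules out saying that the plan has no check at all; it leaves the checks partial.

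The simulated inflation comes from an assumed three- to fivefold difference in calling. Even then, ln 0.91 = −0.094 is small beside a standard error of about 2/√72 = 0.24 for the log hazard ratio. That also stands.

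A reader might infer that the protocol contradicts itself, because Section 8.0 (under Confirmation) says that dropping response confirmation "may increase the importance of central review to protect against bias, in particular in studies which are not blinded". That sentence concerns confirmation of tumour response. It commits the trial to nothing on progression, so it does not support a self-contradiction about PFS.

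**Conclusion.** The gap is real and limited. A stand-alone PFS event has no criteria and is called by an assessor who, on the only plausible reading of Sections 5.2 and 5.4, knows the arm; no planned PFS analysis leaves it out. PFS is therefore open to assessment bias of unknown direction and size.

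It would be tempting to conclude that the bias favours enzalutamide, or that the false-positive rate is 0.14 to 0.19. The documents support neither. Those rates rest on the assumed call shares, 12-month median, time shift, follow-up and one-sided 0.10 level. Section 11.5 sets that level for the primary endpoint only, so no planned PFS decision uses it.

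This is worth correcting because the correction is cheap and must be in place before the data are collected. It does not touch the primary analysis.

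**What to change.** - Add a CRF field recording which component triggered each PFS event.
- Prespecify in Section 11.6.4 a sensitivity PFS limited to PCWG2 PSA progression, RECIST 1.1 progression, new metastatic sites on bone scan as worded in 8.8, or death. Use the same stratified log-rank test and report it beside the 8.8 version, with the number of clinical-only events per arm.
- In that analysis a clinical-only call is not an event. Use objective progression or death documented in the existing 3-monthly follow-up (Section 8.9); otherwise censor at the last objective assessment.
- If the two versions differ materially, interpret the PFS result with caution.

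Written criteria for clinical progression would help, but would not replace the sensitivity analysis, since an assessor who knows the arm would still apply them.

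The direct cost is one CRF field and one further analysis, with no extra visits or tests. There is a statistical cost. Progression is a removal criterion (Section 9.4); after removal the calendar marks only survival and progression, with no PSA, and footnote 3 ties scans to study treatment. Objective evidence after a clinical call will therefore often be sparse. True symptomatic progressions will be counted later or censored, possibly informatively, and later therapy may delay the objective event. Bone-scan reading by the site also keeps some judgement. This is why the added analysis should sit beside the 8.8 version and not replace it.
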